6.1.3 Prior and Concomitant Medication

The dictionary used for coding concomitant medications is the World Health Organization Drug Registration and Listing. Frequency tables displaying frequency of subjects for each drug category summarized by Anatomical Therapeutic Chemical (ATC) and coded terms will

be used to summarize the number and percentage of subjects with prior and concomitant medications. The following time windows will be used:

- Prior medication: medication stopped prior to randomization
- Concomitant medication present in pre-treatment, main treatment, extension period, follow-up period, overall study period, full study period (i.e administered at least one dose within the respective period)
- Concomitant medication started in pre-treatment, main treatment, extension period, follow-up period, overall study period, full study period

Frequency tables of subjects taking prohibited concomitant medications (see study protocol section 6.5) are considered as well as by categories: anticoagulants, antiplatelets (incl. ASA), thrombolytic medication.

6.1.4 Renal Replacement Therapy Baseline Information

Information of the renal replacement therapy at baseline will be evaluated similar to the other baseline characteristics. In this context the use of unfractionated heparins and LMWH for dialysis maintenance at baseline will be descriptively summarized by treatment groups and overall.

6.2 Efficacy

6.2.1 Main efficacy analysis

Two main efficacy variables will be considered. The first is the composite endpoint consisting of the following components:

- Death due to MI, ischemic stroke, pulmonary embolism (PE), non-CNS systemic embolism (SE) and undetermined - presumed cardiovascular death
- Stroke (ischemic stroke or undetermined type)
- MI
- Major amputation of vascular etiology
- Acute limb ischemia
- Symptomatic VTE
- Systemic embolism

The second variable is the thrombosis of the arteriovenous fistulas or grafts.

The analysis for both main efficacy variables is a descriptive time to first event analysis which will be conducted separately for the osocimab low and high dose group similar to the primary safety analysis (i.e. only treatment emergent efficacy events which occurred during the main treatment period will be considered), see section 6.4.1. Thus, the descriptive analysis focuses on estimating the efficacy under constant osocimab concentration during chronic treatment.

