**Table 3–1: Objectives and Endpoints**

Objectives	Endpoints
Primary	

 
To clinically assess the safety and tolerability of different doses of osocimab administered subcutaneously once a month during main treatment period as compared to placebo
 
	
 
Composite of major and clinically-relevant non-major bleeding events (in alignment with ISTH guidelines) as assessed by blinded CIAC
 
Composite of moderate and severe AEs and SAEs
 

Secondary	

 
To assess the change of key PD parameter from baseline
 
	
 
aPTT, FXIa activity at trough levels after 6 months
 

Tertiary/Exploratory	

 
To clinically assess the efficacy of osocimab during main treatment period
 
To evaluate the anticoagulant effect of osocimab on the extracorporeal blood circuit by the assessment of a semi-quantitative clotting score (SQCS)
 
To evaluate the impact of osocimab on the AV access for participants with fistulas or grafts
 
To assess key PK parameter
 
To explore additional PK/PD parameters, biomarkers and biomarker genetics
 
To further investigate the study intervention (i.e. mode-of-action-related effects and / or safety) and to further investigate pathomechanisms deemed relevant to cardiovascular and renal diseases and associated health problems
 
	
 
Composite endpoint consisting of: vascular death [due to MI, stroke, PE and SE], non-fatal stroke, non-fatal MI, major amputation of vascular etiology, acute limb ischemia and symptomatic VTE as assessed by blinded CIAC
 
Incidence of thrombosis of the arteriovenous fistulas or grafts
 
SQCS
 
AV access bleeding score
 
Osocimab trough levels
 
Various biomarkers and biomarker genetics may be explored (e.g., diagnostic, safety, population PK, PD, monitoring, or potentially predictive biomarkers)
 

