### 9.4.3 Secondary Endpoints

The activated partial thromboplastin time (aPTT) and FXIa activity at trough levels after 6 months will be analyzed as ratio to baseline by providing the mean and median, together with the standard deviation and quantiles, respectively.

The exploratory composite efficacy endpoint will be analyzed using a time to event analysis similarly to the primary safety endpoints. Thus, the descriptive analysis focuses on estimating the efficacy under an osocimab concentration which is expected to be maintained during a chronic treatment.

Only events that started after the first dose of study treatment and during the main treatment period are considered for the primary analysis. Events that occurred during the pre-treatment period will be displayed in an exploratory manner.

The endpoint of thrombosis of the arterio-venous grafts or fistulas will be handled similar.

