
 To clinically assess the efficacy of osocimab during main treatment period To evaluate the anticoagulant effect of osocimab on the extracorporeal blood circuit by the assessment of a semi-quantitative clotting score (SQCS) To evaluate the impact of osocimab on the AV access for subjects with fistulas or grafts To assess key PK parameter To explore additional PK/PD parameters, biomarkers, and biomarker genetics To further investigate the study intervention (i.e. mode-of-action-related effects and / or safety) and to further investigate pathomechanisms deemed relevant to cardiovascular diseases and associated health problems 	
 Composite endpoint consisting of: vascular death [due to MI, stroke, PE, and SE], non-fatal stroke, non-fatal MI, major amputation of vascular etiology, acute limb ischemia, symptomatic VTE and systemic embolism as assessed by blinded central independent adjudication committee (CIAC) Incidence of thrombosis of the arterio-venous grafts or fistulas Semi-quantitative clotting score AV access bleeding score Osocimab trough levels Various biomarkers and biomarker genetics may be explored (e.g. diagnostic, safety, population PK, PD, monitoring, or potentially predictive biomarkers)

Abbreviations: AE = adverse event, aPTT = activated partial thromboplastin time, AV = arteriovenous, CIAC = Central Independent Adjudication Committee, ISTH = International Society on Thrombosis and Hemostasis, MI = myocardial infarction, PD = pharmacodynamic(s), PE = pulmonary embolism, PK = pharmacokinetic(s), SAEs = serious adverse events, SE = systemic embolism, SQCS = semi-quantitative clotting score, VTE = venous thromboembolism

The primary objective is to assess the safety under an osocimab concentration which is expected to be maintained during a chronic treatment. Thus, the attributes constituting the primary estimand are the following:

Population: The population consists of ESRD patients, further defined by the in- and exclusion criteria, who received assigned treatment at least once.

Variable:

- Time from first dose of assigned treatment to treatment emergent major and clinically relevant non-major bleeding events (in alignment with ISTH guidelines) up until 30 days after the last administration of assigned treatment
- Time from first dose of assigned treatment to moderate or severe AEs and SAEs up until 30 days after the last administration of assigned treatment

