4.6 Blind Review

There will be two data assessment lists. The first one will occur after primary completion and the second one will occur after end of study. The results of both data lists will be documented in separate lists of important deviations, validity findings and assignment to analysis set(s). Any changes to the statistical analysis prompted by the results of the review of study data will be documented in an amendment and, if applicable, in a supplement to this SAP.

The results of the final data assessment will be documented in the final list of important deviations, validity findings and assignment to analysis sets. Pharmacodynamic values to be excluded from statistical analysis will be documented in the list of pharmacodynamic values to be flagged as invalid.

5. Analysis Sets

Final decisions regarding the assignment of subjects to analysis sets will be made during the review of study data and documented in the final list of important deviations, validity findings and assignment to analysis set(s) (see section 4.6).

The following populations are defined:

Population	Description
Enrolled	All subjects who sign the ICF
Full Analysis Set	All subjects randomly assigned to study intervention.
Safety Analysis Set	All subjects randomly assigned to study intervention and who took at least 1 dose of study intervention. Subjects will be analyzed according to the intervention they actually received.
Pharmacokinetic analysis set	All osocimab-treated subjects with at least 1 PK sample in accordance with the PK sampling schedule (Section 1.3 and Section 8.5 of the study protocol) and without deviation from the protocol that would interfere with the evaluation of the PK data will be included in the PK analysis.
Pharmacodynamic analysis set	All subjects with at least 1 PD sample in accordance with the PD sampling schedule and without deviation from the protocol that would interfere with the evaluation of the PD data will be included in the PD analysis.
Listing only set	All subjects who signed ICF but are not randomized.

In accordance with the “population” attribute of the primary estimand, the primary analysis set is the safety analysis set.

Supplementary analyses of the efficacy variables will be performed on the full analysis set.

6. Statistical Methodology

In general, the evaluations will be conducted on each osocimab group and on the placebo group.

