6.2.2 Supplementary Analyses

Efficacy Analysis for the overall study period and full study period in SAF

Treatment emergent efficacy events occurring in the overall study period (main and extension treatment period) and the full study period (main, extension and follow-up period) will be analysed similarly as the main efficacy analysis.

Efficacy Analysis in FAS

All efficacy events of the main efficacy variables occurring from randomization until the respective periods (main treatment period, overall treatment period and full study period) will be considered. Similar statistical methods will be applied as for the main efficacy analyses, but the intercurrent event “premature discontinuation of treatment” will be handled following the treatment policy strategy.

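### AV fistula or graft thrombosis is analysed in all treated participants, catheter users included, and no planned analysis gives the risk among those with an AV access

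*SAP*

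**What the plan says.** SAP 6.2.1 lists the thromboembolic composite as the first main efficacy variable and then adds: "The second variable is the thrombosis of the arteriovenous fistulas or grafts". On method it says: "The analysis for both main efficacy variables is a descriptive time to first event analysis", to be run like the primary safety analysis of SAP 6.4.1. Protocol 9.4.3 agrees: "The endpoint of thrombosis of the arterio-venous grafts or fistulas will be handled similar".

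On the population, SAP section 5 states that "the primary analysis set is the safety analysis set", meaning everyone randomised who received at least one dose. It continues: "Supplementary analyses of the efficacy variables will be performed on the full analysis set". SAP 6.2.2 extends the time window under the title "Efficacy Analysis for the overall study period and full study period in SAF", again without reference to access type. The efficacy subgroup list in SAP 6.2.4 does not include dialysis access.

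Protocol section 5 places no restriction on vascular access, so catheter users are eligible. Catheter access (yes/no) is a minimisation factor in the more heavily weighted group (Protocol 6.3, SAP 3.1), and it is tabulated at baseline by treatment group (SAP 6.1.1).

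For a related endpoint, the AV access bleeding score, Protocol 8.2.2.1 and the schedule of activities state that the assessment does not apply when a catheter is used. The thrombosis endpoint has no such rule.

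**The concern.** A person with no fistula or graft cannot have one thrombose. Such people nevertheless add participant-years to the incidence rate and heads to the cumulative incidence. SAP 6.4.1, which governs this analysis by cross-reference, asks for exactly these absolute measures: Aalen-Johansen incidences, their differences between arms, and rates per 100 participant-years.

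The published figure would then describe a mixture whose value depends on how many catheter users were enrolled. A reader who wants the risk of access thrombosis in patients who have an access would not find it in any planned table. The protocol describes the trial as preparation for Phase 3 (section 4.1), so an absolute rate that moves with case mix is a weaker planning input than it needs to be.

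**Working it through.** **Is there any restriction?** The main analysis uses the safety set (SAP 5, 6.2.1), the supplementary analyses use the safety and full analysis sets (SAP 5, 6.2.2), and the subgroups do not cover access (SAP 6.2.4). The safety set is reached by cross-reference rather than in one sentence, but nothing in either document removes catheter users.

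**Is there a figure to reproduce?** The plan gives no rate, event count or precision for access thrombosis. The loss-to-follow-up input used below, 15 per 100 participant-years over 6 months, does reproduce the plan's completer count: 600 × (1 − 0.15 × 0.5) = 555.

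**Inputs**
- From the documents: about 200 per group; T = 0.5 years; loss m = 0.15 per year; hazard ratio 0.75, borrowed from the efficacy composite (Protocol 9.2, SAP 9.1).
- Assumed, because the documents do not give them: catheter-only share c of 10% to 40%; thrombosis rate r = 0.20 per year among those with an AV access; zero hazard in catheter users.

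**Formulas**
- Risk among those with an AV access: p = r/(r+m) × (1 − exp(−(r+m)T)). Placebo: 0.20/0.35 × (1 − exp(−0.175)) = 9.17%. Osocimab, with r = 0.15: 0.15/0.30 × (1 − exp(−0.15)) = 6.96%. Difference: −2.21 points.
- Follow-up per catheter user: k = (1 − exp(−mT))/m = (1 − exp(−0.075))/0.15 = 0.482 years.
- Whole-set incidence = (1−c)p. Whole-set rate = (1−c)p / [(1−c)p/r + ck].

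Example for c = 20%, placebo: events 160 × 0.0917 = 14.7; participant-years 14.7/0.20 + 40 × 0.482 = 92.7; rate 15.8 per 100.

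| Catheter-only share | Placebo rate per 100 PY, whole set (AV access: 20.0) | 6-month incidence, whole set (AV access: 9.2%) | Risk difference in points, whole set (AV access: −2.2) | Hazard ratio, whole set (AV access: 0.750) |
|---|---|---|---|---|
| 10% | 17.9 | 8.3% | −2.0 | 0.751 |
| 20% | 15.8 | 7.3% | −1.8 | 0.752 |
| 30% | 13.8 | 6.4% | −1.6 | 0.753 |
| 40% | 11.8 | 5.5% | −1.3 | 0.754 |

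The shortcut rate × (1−c) gives nearly the same: 20 × 0.9 = 18 and 20 × 0.6 = 12. At an assumed 10 per 100 participant-years the relative dilution is similar (c = 20%: 8.0 against 10.0).

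**If catheter share were unbalanced.** With a true hazard ratio of 1.0, the rate formula gives an apparent ratio of about 1.08 for shares of 17% (osocimab) and 23% (placebo), and about 1.14 for 15% and 25%. Minimisation on catheter access is meant to prevent such gaps.

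**If some catheter users do carry a fistula or graft.** If a fraction q of them have one at the same risk, the dilution falls from c to c(1−q). The table is therefore an upper bound for each c.

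**The case against.** The strongest counter-argument is that an all-treated population is a legitimate choice for an exploratory, descriptive endpoint. The envisaged indication covers haemodialysis patients without regard to access (Protocol 4.2), so a whole-population rate is a meaningful quantity. The comparative summary is the hazard ratio, which barely changes. Baseline catheter use is tabulated, so a reader could rescale the absolute figures by 1/(1−c). All of this stands, and it limits the importance of the point. Rescaling is only a rough substitute for reporting the result with its own denominator and interval.

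Four stronger readings are tempting, and the documents do not support them:

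- *The analysis contradicts its own objective.* Protocol Table 3–1 has an objective worded "To evaluate the impact of osocimab on the AV access for participants with fistulas or grafts", and the SAP repeats it: "To evaluate the impact of osocimab on the AV access for subjects with fistulas or grafts". Neither table pairs endpoints with objectives. Read in listed order, thrombosis falls under the unrestricted efficacy objective and the AV bleeding score under this one. Protocol 8.1 also lists thrombosis among the efficacy components.
- *Catheter users cannot have the event.* The recorded factor is the access route in use. A catheter user may have an unused or maturing fistula, which can clot.
- *The treatment comparison is biased.* That needs unequal catheter shares, on a factor the randomisation balances.
- *The result is useless for planning the next phase.* It is usable for a trial admitting all access types with a similar mix.

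**Conclusion.** The point holds as a matter of dilution and missing information. As planned, the absolute measures for this endpoint are understated, relative to participants with an AV access, by up to about the catheter-only share, and no planned analysis supplies the undiluted figure. Under the assumed 10% to 40% share and 20 per 100 participant-years, the reported rate is about 18 down to 12 and the 6-month incidence 8.3% down to 5.5% instead of 9.2%. These sizes rest on assumed inputs and on zero hazard in catheter users. The illustration also leaves out the competing events of death and premature discontinuation.

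The hazard ratio is essentially unaffected while access type is balanced, and the endpoint is exploratory. The change is worth making because it is cheap and because the plan already applies the same logic to the AV bleeding score.

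**What to change.** For this endpoint, add to SAP 6.2.1 and 6.2.2 an analysis in the subset of the safety set, and of the full analysis set, with a fistula or graft at baseline. If the presence of an unused fistula or graft is not recorded, use non-catheter dialysis access at baseline, which is known for every participant from the minimisation. Report the subset's denominators by arm and take the incidence rate, cumulative incidence and risk difference from it. Show the whole-set result alongside, so that events in baseline catheter users are still reported.

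Restricting on a characteristic fixed before dosing keeps the comparison between randomised groups. Letting participants enter the risk set when they acquire an access would not: it selects on a post-randomisation event and needs access-change dates, which the documents do not show are collected. It should be left out, or kept as exploratory only if those dates exist.

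The cost is SAP text and some tables, a smaller denominator, and possibly a few events outside the subset. With the fallback definition no new data are needed. SAP 6.5 indicates that the primary analysis is already complete, so the addition would belong to the final analysis and be labelled as added later; SAP 4.5 allows further post-hoc analyses.

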6.2.2 Supplementary Analyses

Efficacy Analysis for the overall study period and full study period in SAF

Treatment emergent efficacy events occurring in the overall study period (main and extension treatment period) and the full study period (main, extension and follow-up period) will be analysed similarly as the main efficacy analysis.

Efficacy Analysis in FAS

All efficacy events of the main efficacy variables occurring from randomization until the respective periods (main treatment period, overall treatment period and full study period) will be considered. Similar statistical methods will be applied as for the main efficacy analyses, but the intercurrent event “premature discontinuation of treatment” will be handled following the treatment policy strategy.

6.2.3 Other efficacy analyses

Efficacy Analysis by Component

The main efficacy analysis will be repeated for all single components of the main efficacy variable (MI, stroke (ischemic and undetermined type), major amputation of vascular etiology, acute limb ischemia, symptomatic VTE, systemic embolism).

Analysis of Death Events

The main efficacy analysis will be repeated for all-cause death and for vascular death (Death due to MI, ischemic stroke, pulmonary embolism (PE) and non-CNS systemic embolism (SE)). In addition, frequencies of other reasons (including COVID-19 related) will be displayed by the categories as adjudicated by the CIAC.

Pre-Treatment Efficacy Summary

All efficacy events that started after randomization and before first dose of study intervention will be summarized by presenting counts and percentages of subjects by treatment group.

SQCS Analysis

The effect of osocimab on the clotting in the dialysis circuit will be assessed by the SQCS. Clotting scores will be assigned as follows:

- “0” clean filter and no visible clots in the drip chamber/air trap
- “1” traces of coagulation in the filter and/or in the drip chamber/air trap
- “2” intermediate state between “1” and “3”
- “3” fully clotted extracorporeal system resulting in an interruption of the hemodialysis session

Adequate anticoagulation is defined by a SQCS of less or equal “1”.

The mean difference of SQCS values during main treatment period and baseline between each of the osocimab groups and the placebo group by visit will be displayed together with the corresponding 90% (and 95%) confidence intervals applying ANOVA with treatment group as factor. This will also be repeated for the overall study period. The distribution of SQCS between each of the osocimab groups and the placebo group by visit will be compared using

the Wilcoxon Rank sum test. Change in SQCS scores from baseline per visit will be also calculated. Baseline will be the median of all pre-treatment values.

Percentage of subjects with adequate anticoagulation (SQCS "0" or "1") by visit will be presented.

Additionally, a table will be created showing SQCS categories over time per visit, at pre-treatment all values will be shown. This will be done for the full study period. Figures will be provided.

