## 4. Study Design

### 4.1 Overall Design

Study 20115 is a covariate-adaptive randomization, double-blind, parallel group, placebo-controlled, multi-center study to assess the safety and tolerability of monthly administrations of a low and high dose cohort of osocimab given subcutaneously in ESRD patients on hemodialysis. In this protocol, the term hemodialysis includes hemodiafiltration. The overall study design is depicted in [Figure 1–1](#).

Approximately 600 participants (up to 750) from approximately 150 sites are planned to be randomized and will receive either osocimab (200 participants on each dose arm), or placebo (200 participants, i.e. 100 participants receiving low dose volume placebo and 100 participants receiving high dose volume placebo).

The following regions are planned to be included: North America, Europe, Asia Pacific.

The planned study will consist of:

- **Screening period (visit 1):** up to 14 days
- **Randomization (visit 2):** 1 day
- **Pre-treatment period (from visit 2 until visit 4):** 7 days
- **Main treatment period (from visit 5 until EOMT visit):** 6 months
- **Extension treatment period (from visit 19 until EOET visit):** up to 12 months
- **Follow-up period (from visit 32 until visit 35):** 4 months after end of treatment (EOMT or EOET)

Informed consent form will be obtained at the beginning of the screening period. During the screening period, participant's eligibility evaluations will be performed. Participants will be randomized either to osocimab or to placebo using a covariate-adaptive randomization technique (minimization methods) (for details see Section 6.3).

During the pre-treatment period, which will serve as a baseline period, a series of 3 hemodialysis sessions will be performed. Unfractionated or low molecular weight heparin (UFH/LMWH) is allowed as anticoagulation for maintenance of hemodialysis treatment during the whole study duration.

The study intervention will be administered subcutaneously abdominal with one single loading dose at visit 5 and monthly maintenance doses from visit 8 onwards until the end of the extension treatment period with an overall maximum of 18 months of treatment. The main treatment period consists of 6 months of treatment as this time frame is deemed to be the minimum clinically relevant treatment time to assess osocimab as chronic life-time treatment in an appropriate manner and in preparation for Phase 3.

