### 8.2.2.1 Assessment of AV Access Bleeding

Severity of bleeding at the dialysis access will be assessed approx. 15 minutes after removal of the dialysis needle(s) from the AV access according to the following categories (exploratory bleeding score):

- “0” no access bleeding
- “1” slow oozing
- “2” overt bleeding

In case the AV access exhibits overt bleeding 15 minutes after removal of the dialysis needle(s) (AV access bleeding score of 2), the investigator may consider the reduction of heparin (i.e. UFH, LMWH) for the subsequent dialysis sessions during the treatment and follow-up period. For such decision, the investigator should take all available participant information into account (e.g., laboratory values, concomitant medication, details of hemodialysis session, adverse events etc.).

In case catheter is used, the AV access bleeding is not applicable.

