 - Probable fatal bleeding; no autopsy or imaging confirmation but clinically suspicious

- Type 5b:
 - Definite fatal bleeding; overt bleeding or autopsy or imaging confirmation

Bleeding Characteristics Summary

The characteristics of all bleedings will be summarized by presenting counts and percentages of events with a certain attribute separated by treatment group.

Pre-Treatment Safety Summary

All safety events that started after randomization and before first dose of study intervention will be summarized by presenting counts and percentages of subjects with efficacy event before start of treatment separated by treatment group.

AV Access Bleeding Score Analysis

Severity of bleeding at the dialysis access will be assessed approx. 15 minutes after removal of the dialysis needle(s) from the AV access according to the following categories (exploratory bleeding score):

- “0” no access bleeding
- “1” slow oozing
- “2” overt bleeding

The mean difference of AV access bleeding score during main treatment period and baseline between each of the osocimab groups and the placebo group by visit will be displayed with the corresponding 90% (and 95%) confidence intervals applying ANOVA with treatment group as factor. The distribution of AV access bleeding score between each of the osocimab groups and the placebo group by visit will be compared using the Wilcoxon Rank sum test. Change in AV access bleeding scores from baseline per visit will be also calculated. Baseline will be the median of all pre-treatment values.

Additionally, a table will be created showing AV access bleeding categories over time per visit, at pre-treatment all values will be shown. Change from baseline per visit will be calculated. This will be done for the full study period. Figures will be provided.

Furthermore, the difference of the proportion of hemodialysis sessions with no AV access bleeding during main treatment period and baseline between each of the osocimab groups and the placebo group will be summarized with the corresponding 90% (and 95%) confidence intervals based on the score method as described by Newcombe (1998).

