6.4.8 Hemodialysis data

Hemodialysis data like heparin dose and Kt/V will be displayed by means of descriptive statistics and change from baseline by visit.

Furthermore, the difference of the proportion of hemodialysis sessions with adequate anticoagulation during main treatment period and baseline between each of the osocimab groups and the placebo group will be summarized with the corresponding 90% (and 95%) confidence intervals based on a proportion test.

Additionally a table will be created showing all heparin values over time per visit, at pre-treatment all values will be shown. Change from baseline per visit will be calculated. Baseline in this case will be the mean of all pre-treatment values. This will be done for the full study period.

Any changes to the dialysis prescription and compliance will be summarized by visit and treatment group.

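### SQCS and AV access bleeding score: the treatment-only ANOVA omits the baseline score as a covariate and does not say whether raw or change scores are analysed, at a modest cost in precision

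*SAP*

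**What the plan says.** For the clotting score, SAP 6.2.3 describes the compared quantity as "The mean difference of SQCS values during main treatment period and baseline between each of the osocimab groups and the placebo group by visit", with 90% and 95% "confidence intervals applying ANOVA with treatment group as factor". A Wilcoxon rank sum test by visit accompanies it. The section then adds: "Change in SQCS scores from baseline per visit will be also calculated". The baseline is defined: "Baseline will be the median of all pre-treatment values".

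SAP 6.4.3 uses the same model, the same test and the same median baseline for the AV access bleeding score: "Change in AV access bleeding scores from baseline per visit will be also calculated". Neither section puts the baseline score, heparin dose or a minimization factor into the model.

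The baseline data are planned. Protocol 4.1 says that in the pre-treatment period "a series of 3 hemodialysis sessions will be performed", and the schedule of activities (Protocol Table 1-1) lists both scores and heparin dose at visits 2 to 4. The AV access score is not recorded for everyone (Protocol 8.2.2.1): "In case catheter is used, the AV access bleeding is not applicable". Heparin for dialysis is allowed, not required. SAP 6.4.8 forms a pre-treatment heparin value, "Baseline in this case will be the mean of all pre-treatment values", but uses heparin only in descriptive tables.

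Protocol 9.4.4 describes something else for both scores: a difference in medians with an interval from a t-test.

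**The concern.** Two things are unsettled. First, the response is ambiguous. The wording of the compared quantity can mean treatment-period minus baseline differences, or raw scores shown for both periods. The separate sentence saying that change is also calculated does not decide it.

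Second, neither reading uses the pre-treatment scores in the most efficient way. A raw-score ANOVA ignores what the baseline says about each participant. A change-score ANOVA fixes the baseline coefficient at 1, which adds baseline noise and over-corrects chance imbalance when the scores are only moderately correlated. ANCOVA estimates the coefficient from the data and, in large samples, is no less precise than either.

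In a descriptive trial the estimates and intervals are the result. These two scores serve stated exploratory objectives: the anticoagulant effect in the extracorporeal circuit, and the effect on the AV access.

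**Working it through.** **Inputs from the documents.** 600 randomized, 200 in each analysed group (Protocol 4.1); loss to follow-up 15 per 100 participant-years, 6 months, 555 completers (Protocol 9.2); three pre-treatment sessions (Protocol 4.1). No standard deviation, interval width or correlation is given for either score.

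**Reproducing the plan's figure.** 600 × (1 − 0.15 × 0.5) = 555; the exponential form, 600 × exp(−0.075), gives 556.6. The stated 555 reproduces, so each group has 555/3 = 185 completers.

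**Assumptions.** Each session's score has variance 1 (results are in SD units), and any two sessions of one participant have correlation ρ, from 0.2 to 0.8. The baseline is taken as the mean of three sessions for the closed form.

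**Formulas.** The baseline variance is (1 + 2ρ)/3 and its covariance with an on-treatment session is ρ. Hence:

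- raw score: variance 1
- change score: 1 + (1 + 2ρ)/3 − 2ρ = (4/3)(1 − ρ)
- ANCOVA residual: 1 − ρ²/[(1 + 2ρ)/3] = 1 − 3ρ²/(1 + 2ρ)
- 90% half-width: 1.645 × √(2v/185), with v the variance above

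Example at ρ = 0.5: change (4/3)(0.5) = 0.667; ANCOVA 1 − 0.75/2 = 0.625; √(0.625/0.667) = 0.968, so the interval is 3.2% narrower than for change. √0.625 = 0.791, so it is 20.9% narrower than for raw scores.

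| ρ | Change variance | ANCOVA variance | Half-width raw / change / ANCOVA | Narrower than change | Narrower than raw |
|---|---|---|---|---|---|
| 0.2 | 1.067 | 0.914 | 0.171 / 0.177 / 0.164 | 7.4% | 4.4% |
| 0.3 | 0.933 | 0.831 | 0.171 / 0.165 / 0.156 | 5.6% | 8.8% |
| 0.5 | 0.667 | 0.625 | 0.171 / 0.140 / 0.135 | 3.2% | 20.9% |
| 0.7 | 0.400 | 0.388 | 0.171 / 0.108 / 0.106 | 1.6% | 37.8% |
| 0.8 | 0.267 | 0.262 | 0.171 / 0.088 / 0.087 | 1.0% | 48.9% |

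Setting (4/3)(1 − ρ) = 1 gives ρ = 0.25. Below that, the change score is less precise than the raw score.

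**Check with the SAP's own baseline.** The SAP takes the median, and the score is ordinal. A 0-3 score was simulated with a median-of-three baseline under two assumed distributions over the categories 0 to 3: (0.40, 0.45, 0.13, 0.02) and (0.70, 0.25, 0.04, 0.01). The latent correlations were 0.3, 0.5, 0.7 and 0.85.

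| Distribution | Single-session correlation | Narrower than change | Narrower than raw |
|---|---|---|---|
| First | 0.25 / 0.41 / 0.59 / 0.73 | 13.1 / 9.5 / 6.8 / 4.7% | 4.9 / 12.4 / 23.6 / 36.0% |
| Second | 0.21 / 0.37 / 0.55 / 0.71 | 12.9 / 9.6 / 6.9 / 4.8% | 3.4 / 9.9 / 20.8 / 33.4% |

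The gain over change is larger than in the closed form because a median of three coarse scores is a noisier quantity to subtract. At a single-session correlation of 0.41 the simulated change variance is 0.94 of the raw variance, against (4/3)(1 − 0.41) = 0.79 for a mean baseline.

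**Not computed.** The 0-2 AV access score was not simulated. Its intervals will be wider than the half-widths above because catheter users have no score, and their share is not stated. The gain from heparin dose cannot be computed, since no correlation with either score is given.

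**The case against.** The strongest reply is that the stakes are small. Both scores are tertiary/exploratory, and Protocol 9.1 makes every analysis descriptive. The secondary aPTT and FXIa endpoints measure the anticoagulant effect at a higher level. Wilcoxon tests, category tables and the percentage with adequate anticoagulation are also planned. Under randomization a treatment-only contrast has no systematic bias; chance imbalance is what the interval covers. All of this stands and limits the consequence to precision.

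A second reply concerns timing. SAP 6.5 states that the primary analysis was complete before that section was written, and SAP 4.4 says that it unblinded the study. A new main-period model would therefore be post hoc. This also stands, and it governs how the adjusted analysis should be labelled.

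A reader might infer more than the documents support:

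- **That the pre-treatment scores are discarded.** They are not: the SAP builds a baseline from them and calculates change. If change is the response and correlation is 0.5 or more, subtraction already captures most of the gain under a mean baseline.
- **That all participants have the data.** Catheter users have no AV access score, and some participants may receive no heparin.
- **That omitting heparin dose is a serious flaw.** The documents do not rank heparin among the determinants of either score or give a correlation. A weak covariate need not help in a finite sample, and the baseline score may already carry part of any stable heparin effect.
- **That the largest figures apply.** They require the raw-score reading with a high correlation. A correlation of 0.1 would raise the change-score figure to 9.9%, but the documents give no basis for choosing it.

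None of this shows that adjusting for the baseline score would be wrong or costly.

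**Conclusion.** The point holds as a modest one about precision and clarity. The response is not defined, and the baseline score is used for subtraction at most, never as a covariate. With a mean-of-three baseline and an assumed correlation of 0.2 to 0.8, adjustment narrows the interval by about 1-7% if change is analysed and about 4-49% if raw scores are. With the SAP's median baseline on a simulated 0-3 score the ranges are about 5-13% and 3-36%. The direction rests on large-sample theory. The size rests on the assumed correlations and score distributions, and above all on which response the SAP intends. The gain is narrower descriptive intervals and correction of chance baseline imbalance. No systematic bias is removed, and no primary or secondary result is affected.

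**What to change.** In SAP 6.2.3 and 6.4.3, state the response and replace the treatment-only ANOVA by ANCOVA of the visit score on treatment group and baseline score. Report adjusted mean differences with 90% and 95% confidence intervals. Once the same baseline is a covariate, raw and change responses give the same treatment difference and interval, so the ambiguity loses its effect. For the AV access score, restrict the analysis to participants without catheter access. Keep the Wilcoxon test as support.

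Pre-treatment heparin dose may be added as an optional covariate, with separate terms for unfractionated and low molecular weight heparin and a stated rule for non-users. On-treatment dose should never be used: Protocol 8.2.2.1 lets the investigator consider reducing heparin after overt access bleeding, so that dose can respond to the outcome.

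The same edit should reconcile the SAP with the medians and t-test of Protocol 9.4.4, and explain why these scores use a median baseline when the general rule in SAP 4.5 is a mean.

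Label the adjusted main-period analysis supplementary, since the primary analysis was already complete; SAP 4.5 allows additional post-hoc analyses. The core change costs SAP wording and a short program, with no new data. The heparin option needs somewhat more work.
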